	Peak Troponin-T and CKMB	During admission
	Safety: Incidence of adverse events the first seven days of index event	Within 7 days of STEMI

Exploratory endpoints:

1. Pre-PCI and post-PCI TIMI flow
2. C-reactive protein (CRP), leucocyte- and differential count, thrombocytes, HbA1c, p-Glucose, pro-brain natriuretic peptide (BNP), creatine kinase, creatinine, potassium, and sodium at admission, during admission and after 3 months
3. Arrhythmia (ventricular tachycardia/ventricular fibrillation) during transportation in the ambulance and peri-procedural during PCI
4. Bolus CFR, IMR, absolute CFR, and microvascular resistance reserve (MRR) following primary PCI
5. LVEF on transthoracic echocardiography during admission and one to three months following primary PCI
6. Killip Class at admission

7. Biomarkers of inflammation at admission, 24 hours after admission, and after 3 months
8. All-cause mortality and hospitalization for HF after 1 and 10 years

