### Statistical Analysis

Due to the inclusion and randomization in the prehospital setting, post-randomization exclusions of patients who do not fulfill criteria is expected. The post-randomization exclusions will include patients who are not eligible or patients with other reasons for ST-segment elevation. A differentiation between a classic type 1 acute myocardial infarction with plaque rupture and thrombosis formation and a type 2 acute myocardial infarction with other reasons for ST-segment elevation (e.g. takotsubo, myocarditis, pericarditis, spontaneous coronary artery dissection, coronary embolism, coronary spasm, anemia, etc.) can only be made after further evaluation including initial coronary angiogram and thus after inclusion. Patients included and subsequently excluded will not be included in the modified intention-to-treat population. The modified intention-to-treat population is prespecified and will not be changed during the trial.

Analyses for the primary and secondary outcomes will be performed in the modified intention-to-treat population. Thus, safety including adverse events and serious adverse events and reactions will be assessed in all randomized patients which will be included in the Supplemental Material. Safety in all randomized patients will be further analyzed by calculating a cumulative incidence curve of all-cause mortality at three months which will be included in the Supplemental Material.

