The primary outcome will be tested for normality using Q-Q plot to identify if the observed data is approximate to the expected data. If the primary outcome is normally distributed, mean and standard deviation (SD) will be presented using a Student's t-test to test for differences between treatment groups, whereas median and interquartile range (IQR) and Wilcoxon Rank Sum test will be used if the primary outcome is not normally distributed. Each continuous secondary outcome will be tested for normality and will be presented as either mean and SD or median and IQR. Categorical outcomes will be presented as frequencies and percentages. To assess safety in all randomized patients, the cumulative incidence of adverse events, serious adverse events, and serious adverse reactions will be tested for differences between groups using Chi-Square or Fisher's exact test. Cumulative incidence curve will be calculated for all-cause mortality. Using a Fine and Gray model, hospitalization for heart failure will be analyzed with death considered as a competing risk.

Reporting of effect sizes was not prespecified in the protocol. For effect sizes of efficacy outcomes, mean differences with 95% confidence interval (CI) will be calculated if parametric. For non-parametric numeric outcomes, Wilcoxon-Mann-Whitney odds ratio will be calculated including 95% CI (ties are equally split between groups). To present a change in percent, the effect size for troponin-T and creatine kinase-MB will be calculated using linear regression following log transformation. The effect size of categorical efficacy outcomes will be calculated as relative risk ratios and the 95% CI will be calculated using the Wald method. For all-cause mortality and hospitalization for heart failure, the relative risk will be calculated using Cox proportional hazard analysis and presented as hazard ratios with 95% CI. Hospitalization for heart failure will be calculated with death considered as a competing risk.

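### Adverse events, SAEs and serious adverse reactions are compared between arms by a P-value alone; the SAP should prespecify an effect estimate with a confidence interval in all randomised patients

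*SAP*

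**What the plan says.** Table 1 in Protocol section 5 lists a secondary safety endpoint: "Safety: Incidence of adverse events the first seven days of index event". The SAP, under Statistical Analysis, assesses safety in all randomised patients and analyses primary and secondary outcomes in the modified intention-to-treat population.

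The comparative method for safety is a single sentence. It covers all three categories (any event, serious events and serious reactions) and says of them that they "will be tested for differences between groups using Chi-Square or Fisher's exact test". Just before it the SAP says: "Categorical outcomes will be presented as frequencies and percentages".

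The next paragraph deals with effect sizes. It notes that the protocol did not prespecify any, and then supplies them for efficacy. For numeric outcomes: "For effect sizes of efficacy outcomes, mean differences with 95% confidence interval (CI) will be calculated if parametric". For categorical outcomes: "The effect size of categorical efficacy outcomes will be calculated as relative risk ratios and the 95% CI will be calculated using the Wald method". Death and heart-failure hospitalisation are to be "presented as hazard ratios with 95% CI".

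For mortality in the safety population the SAP says: "Safety in all randomized patients will be further analyzed by calculating a cumulative incidence curve of all-cause mortality at three months". It names no interval or contrast there. Protocol section 10.2 offers chi-square or Fisher's test for categorical variables and a two-tailed 0.05 level. Neither document gives an expected adverse event rate, a safety margin, or a rule for reading a non-significant safety test.

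**The concern.** A test of difference asks whether harm has been shown. A safety reader mostly wants to know how much harm has been excluded, and only an interval answers that. The SAP gives efficacy outcomes an estimate and an interval but leaves the three named safety outcomes with a P-value beside raw counts.

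This matters more than usual here. The trial was sized only on infarct size. Patients are treated before consent, partly on the argument in Protocol sections 9.1 and 9.2.1 that the drug carries no known risk, while section 13 lists death, infection, gastroduodenal ulcer and anaphylaxis among events that could be related to it. For an uncommon harm, P above 0.05 is the likely result whether or not the risk has doubled.

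**Working it through.** **The plan's own figure.** Inputs from SAP Sample Size and Protocol section 10.1: mean 13%, SD 9%, 20% relative reduction (0.20 × 13 = 2.6 points), two-sided 0.05, 80% power.

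n per arm = 2 × [(1.960 + 0.842) × 9 / 2.6]² = 188.1, rounded up to 189, so 378 in total. This matches. No corresponding calculation exists for safety.

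**Number available for safety.** Protocol section 10.1 expects 530 randomised, and section 8.3 gives 1:1 allocation, hence 265 per arm. Recruitment continues until 378 have had the three-month scan, so more may be randomised. At the protocol's 40% drop-out, 378 / 0.6 = 630, or 315 per arm, which serves as the upper case.

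**Power of the planned tests to detect a doubling.** The control rates are assumptions. Power is the sum, over all pairs of event counts from two independent binomials, of the probability of each pair for which the test gives P < 0.05 two-sided. The level is the general one in Protocol section 10.2; the SAP sets its 0.050 threshold only for the primary outcome.

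| Control → treated | Chi-square power, 265/arm | Missed | Fisher power, 265/arm | Chi-square power, 315/arm |
|---|---|---|---|---|
| 1% → 2% | 14% | 86% | 7% | 17% |
| 2% → 4% | 27% | 73% | 19% | 31% |
| 3% → 6% | 38% | 62% | 32% | 45% |
| 4% → 8% | 49.7% | 50.3% | 43% | 58% |
| 5% → 10% | 60% | 40% | 54% | 68% |
| 10% → 20% | 91% | about 10% | 88% | 95% |

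By the normal approximation, power passes 50% at a control rate of about 4.1% with 265 per arm and about 3.5% with 315. For scale, 80% power for 2% against 4% would need 1141 per arm.

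**What an interval would add.** Take 8/265 on placebo and 16/265 on methylprednisolone.

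- Chi-square = 530 × (8 × 249 − 16 × 257)² / (265 × 265 × 24 × 506) = 2.79, P = 0.095. Fisher P = 0.14.
- Relative risk = 16/8 = 2.0. SE of the log = √(1/8 − 1/265 + 1/16 − 1/265) = 0.424. 95% CI = 2.0 × exp(±1.96 × 0.424) = 0.87 to 4.59.
- Risk difference = 8/265 = 3.0 points. SE = √(0.0302 × 0.9698/265 + 0.0604 × 0.9396/265) = 0.0180. 95% CI = −0.5 to +6.5 points.

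With 5 events in each arm, P = 1.00, and the same log formula gives a relative risk of 1.0 with 95% CI 0.29 to 3.41. A P-value of 1 therefore sits beside an upper limit above a tripling. These intervals are Wald-type and only illustrative; a score or exact method is preferable at such counts.

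**The case against.** - **Nothing says a non-significant test will be reported as absence of a safety signal.** A reader might infer that it will. The documents contain no such statement, no equivalence claim for safety and no decision rule, so that would be a prediction about how results will be worded. It stands only that the plan contains no guard against this reading.
- **The information is not withheld.** Counts and percentages per arm are planned, and anyone can compute an interval from them, as above. It would be wrong to say that the plan reports nothing from which the uncertainty can be seen. What is missing is a prespecified estimate.
- **Death and heart-failure hospitalisation do have hazard ratios with intervals.** That sentence names no population. Because both are secondary outcomes (Protocol Table 1), and the SAP analyses secondary outcomes in the modified intention-to-treat set, the intervals appear to belong there and not to all randomised patients. This is an inference, though a fair one. Even so, two of the gravest outcomes will have an interval in the main analysis set.
- **The miss rates depend on assumed rates.** A reader might conclude that the trial would miss a doubling of serious events in general. The documents do not support that. Section 13.2 counts any hospitalisation, prolongation of hospitalisation or death up to one year as an SAE, and section 2.2 cites about 10% one-year mortality and 22% heart failure. A pooled SAE rate of 4% or less is hard to square with those figures. Nor can any multiple be put on infection, since no infection rate is given.
- **This is a proof-of-concept trial with a data safety monitoring board.** Sizing it for infarct size alone is no defect, and adding an interval leaves every power figure unchanged. Both statements are correct. The remedy concerns what is reported, not what can be detected.

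**Conclusion.** The point holds in a limited form. For the three safety outcomes named in the SAP, in the population chosen for safety, the only prespecified comparison is a difference test alongside counts and percentages. Mortality in that population has a curve and no interval. That test says little about the size of harm excluded when events are uncommon. At 265 per arm a doubling is missed more often than not for control rates up to about 4%, or about 3.5% at 315 per arm. The conclusion does not extend to common pooled categories: at a 10% control rate only about one doubling in ten is missed.

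The figures rest on assumed control rates, a two-sided 0.05 level and equal arms. The reading of the test-only rule rests on the SAP's text alone. This is a worthwhile correction to the choice of safety analysis; it does not threaten the trial's primary conclusion.

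**What to change.** In the SAP's Statistical Analysis section:

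1. For adverse events, serious adverse events and serious adverse reactions in all randomised patients, make the risk difference and/or relative risk (methylprednisolone against placebo) with 95% CI the main safety comparison, using a score or exact interval when counts are small.
2. For three-month all-cause mortality in all randomised patients, report a risk difference or hazard ratio with 95% CI beside the cumulative incidence curve, and name the population to which the planned hazard ratios apply.
3. Keep the chi-square or Fisher P-value as descriptive. State that a non-significant result is not evidence of safety and that the upper confidence limit will accompany any safety statement.

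The cost is a few sentences and a few lines of code on data already collected, with no extra patients or procedures. The downside is that wide upper limits will be visible and safety statements will be correspondingly more guarded.
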